## 2. LIST OF ABBREVIATIONS AND DEFINITIONS OF TERMS

Abbreviation	Term
AA	Alopecia Areata
AE	Adverse Event
ALT	Alanine aminotransferase
ANCOVA	Analysis of Covariance
ANOVA	Analysis of Variance
AST	Aspartate aminotransferase
AT	Alopecia Totalis
AU	Alopecia Universalis
BID	Twice-daily
BUN	Blood Urea Nitrogen
°C	Degrees Centigrade
CD	Cluster of Differentiation
CEA	Clinician's Eyebrow Assessment
CMV	Cytomegalovirus
CRA	Clinical Research Associate
CRF	Case Report Form
CS	Clinically Significant
DMARDs	Disease modifying anti-rheumatic drugs
DPCP	Diphenylcycloprophenone
e.g.	for example (Latin; exempla gratia )
EC	Ethics Committee
ECG	Electrocardiogram
eCRF	Electronic Case Report Form
EHL	Eyebrow Hair Loss
°F	Degrees Fahrenheit
FDA	Food and Drug Administration
G	Gram
GCP	Good Clinical Practice
HEENT	Head, Eye, Ear, Nose and Throat
HIPAA	Health Insurance Portability and Accountability Act of 1996
HIV	Human Immunodeficiency Virus
IB	Investigator's Brochure
ICF	Informed Consent Form

CONFIDENTIAL  
Page 13 of 57

Abbreviation	Term
ICH	International Conference on Harmonization
i.e.	that is (Latin; id est)
IFN	Interferon
IL	Interleukin
IRB	Institutional Review Board
IUD	Intrauterine Device
IUS	Intrauterine Hormone Releasing System
JAK	Janus Kinase
LDH	Lactate Dehydrogenase
LTA	Local Tolerability Assessment
LOCF	Last Observation Carried Forward
MedDRA	Medical Dictionary for Regulatory Activities
MHC	Major Histocompatibility Complex
ml	Milliliter
Mm	Millimeter
NCS	Not Clinically Significant
NK/ NKG	Natural Killer/ Natural Killer Group
OTC	Over-The-Counter
PDT	Photodynamic Therapy
PUVA	Psoralen and Ultraviolet A
SADBE	Squaric acid dibutyl ester
SAE	Serious Adverse Event
SEA	Subject's Eyebrow Assessment
SES	Subject's Eyebrow Satisfaction
SI	Subject Identifier
SOP	Standard Operation Procedure
STAT	Signal Transducer and Activator of Transcription
TEAE	Treatment Emergent Adverse Event
Tyk2	Tyrosine Kinase 2
UPT	Urine Pregnancy Test
US	United States
UVA	Ultraviolet A
UVB	Ultraviolet B
WOCBP	Women of childbearing potential

CONFIDENTIAL  
Page 14 of 57

### 3. INTRODUCTION

Aclaris Therapeutics, Inc. is developing ATI-50002 Topical Solution for the treatment of alopecia areata. ATI-50002 is a potent, highly selective inhibitor of Janus kinase 1 (JAK 1) and Janus kinase 3 (JAK 3).

#### 3.1. Summary

##### Overview of Alopecia Areata

Alopecia areata (AA) is an autoimmune dermatologic condition which in its mildest form is typically characterized by patchy non-scarring hair loss on the scalp and/or body. More severe forms of AA include total scalp hair loss, known as alopecia totalis (AT), and total loss of all the hair on the scalp and body, importantly, including loss of eyebrows, eyelashes, and intranasal hair-known as alopecia universalis (AU). While spontaneous regrowth of hair is common in the milder form of AA (patchy), where the hair loss may wax and wane, in patients with the extensive hair loss of AT or AU, spontaneous hair regrowth is rare. AA affects both males and females across all ethnic groups and is the most prevalent autoimmune disease in the United States, with a lifetime risk of 1.7% (Safavi 1995). About two-thirds of affected individuals are 30 years old or younger at the time of disease onset.

The course of AA is unpredictable and while up to 50% of patients may recover within 1 year even without treatment, most patients will have more than one episode of hair loss (Price 2008). Factors portending a poorer prognosis for regrowth are: more extensive hair loss presentations (extensive AA, AT, AU), an ophiasis pattern of hair loss, a long duration of hair loss, a positive family history, the presence of other autoimmune diseases, nail involvement, and young age of first onset (Tosti 2006, Weise 1996). In children, the disease may have a tendency towards worsening with time, even if the initial presentation was mild and the progressively disfiguring nature of the disease can be psychologically devastating. AA is highly associated with numerous psychiatric comorbidities including adjustment disorders, anxiety disorders and depression in both children and adults, and an effective treatment for AT and AU, the more severe forms of the disease, represents a significant unmet medical need (Bilgic 2014, Ruiz-Doblado 2003, Alkhalifah 2010).

The clinical development of innovative therapies in AA has lagged far behind other autoimmune conditions and there are currently no evidence-based treatments for AA. A Cochrane database review highlighted that few therapies for AA have been comprehensively evaluated in randomized clinical trials and that no treatment has demonstrated significant benefit compared to placebo according to evidence-based assessment (Delamere, 2008). This lack of good evidence-based data remains a challenge for physicians attempting to select efficacious treatments for their patients and, as a result, numerous approaches to treatment exist and are typically based on considerations such as the age of the patient, the extent and/or duration of the disease, patient expectations, cost considerations (both time and financial resources) and physician preferences and experience.

Common treatments for the less severe (patchy) form of AA include corticosteroids, either topically applied or injected intralesionally into the alopecic areas, or the induction of an allergic reaction at the site of hair loss using a topical contact sensitizing agent - an approach known as

topical immunotherapy, typically with the topical contact sensitizers diphenylcycloprophenone (DPCP), squaric acid dibutyl ester (SADBE), or treatment with topical anthralin. While these same treatment options may be utilized for the more severe forms of AA, their use in the more severe forms of AA is limited not only due to limited efficacy, but also because of the impracticality of using them over extensive body surface areas. Additional treatments used for extensive forms of AA (AT, AU), have included systemic steroids (pulsed or chronically administered), immunosuppressive agents such as cyclosporine or methotrexate, phototherapy with psoralen +UVA (PUVA), narrow-band UVB, photodynamic therapy (PDT), laser therapy (e.g., excimer laser, fractional photothermolysis lasers), prostaglandin analogs, etanercept, bexarotene and others, all with varying degrees of success and each with its inherent risk of adverse effects and unproven efficacy (Alkhailah 2010, Price 1999, Hordinsky 2015, Strober 2005). Most recently, however, a breakthrough in the understanding of the pathophysiology of AA and several case reports in the literature have suggested that a group of inhibitors of the JAK-STAT pathway, the Janus Kinase (JAK) inhibitors, or “jakinibs” may be efficacious in the treatment of AA even in its most severe phenotypes, AT and AU (Jabbari, 2015, Pieri, 2015, Xing 2014).

The JAKs, are members of a family of tyrosine kinases that are involved in cytokine receptor signaling. The JAK family of enzymes (JAK1, JAK2, JAK3, Tyk2) plays an essential role in regulating the signaling process of most cytokines in cells by linking the cytokine induced signaling from the cell surface membrane receptors to signal transducers and activators of transcription, or STATs, within the cells. Once these JAK receptors are activated by the binding of a cytokine to the appropriate receptor, they initiate a JAK-STAT signaling pathway which can modify gene expression and modulate important regulatory functions in the cell, including regulating immune and inflammatory responses. JAK1 and JAK3 are constitutively associated with the alpha chain and the common gamma chain ( $\gamma c$ ), respectively, of the receptors for interleukin-2 (IL2), interleukin-4 (IL-4), interleukin-7 (IL-7) interleukin-9 (IL-9), interleukin-15 (IL-15), and interleukin-21 (IL-21). When these cytokines bind to their respective receptors, JAK1 and JAK3 are activated and initiate a signaling cascade that drives key inflammatory events, including lymphocyte activation and proliferation. The JAK inhibitors can block the cytokine receptor signaling pathways, (in this instance JAK1 and JAK3) blocking JAK-STAT transcription activation, and can therefore modulate inflammatory or immune responses, which can be beneficial in a variety of disease states, particularly, as recently reported, AA (Xing 2014). In that report, pharmacologic inhibition of JAK kinase signaling (JAK-STAT signaling) was reported to promote hair growth in both genetic mouse models of alopecia and in human subjects.

### **Immunopathology & Pathophysiology of AA**

AA results from an autoimmune attack on the hair follicles that results in growing anagen-phase terminal hairs being induced to prematurely enter the telogen-phase and then shed. In its most acute state, AA demonstrates a histopathologically characteristic white cell infiltrate, the so called “swarm of bees”, encircling the human hair follicle, though more chronic forms typically demonstrate a more sparse infiltrate (Jabbari 2016, Whiting 2003). Though the exact autoantigens expressed in the perifollicular epithelium that allow these specific T-cells to infiltrate the normally immunologically privileged hair follicle have been unknown, the T-cells that home to the hair follicle have been demonstrated to consist of both CD4 and CD8 cells. Most recent studies have further characterized a specific subpopulation of activated NKG2D-bearing CD8 T cells as being

CONFIDENTIAL  
Page 16 of 57

prominent in the peribulbar infiltrate, and it is now currently felt that these CD8+NKG2D+ effector T cells preferentially localize to dermal sheath cells aberrantly expressing high levels of MHC molecules and NKG2D ligands. Interferons, as key activators of the MHC locus and of the cellular immune response, appear to play a key role in eliminating the immunologic privilege of the hair follicle and in inducing and maintaining the pathologic inflammatory response in AA. This is also seen in the C3H-HeJ mouse model of AA, in which IFN- $\gamma$  is required for pathogenesis, and in which administration of IFN- $\gamma$  accelerates disease (Gilhar 2005, Hirota 2003).

AA has been viewed as a Th1-driven disease and, consistent with a pathogenic cellular immune response, elevated Th1 cytokines/ chemokines (IFN-induced chemokines [IP-10/CXCL10]) are seen in the peripheral blood of AA patients and IFN-inducible gene signatures have been described in the skin of AA patients and may correlate with disease activity (Arca 2004, Barahmani 2009, Kuwano 2007). Additionally, transcriptional profiles in human AA patients have shown a Type I IFN response in lesional biopsies and Th1 skewing and elevated IFN response cytokines/chemokines in both the peripheral blood and in reviewed scalp biopsies (Jabbari 2015, Xing 2014, Jabbari 2016). The cellular source of IFN- $\gamma$  is hypothesized to be the T cells as in the AA mouse model IFN-gamma producing CD8+NKG2D+ cells dominate the dermal hair follicle infiltrate, and in human AA, IFN- $\gamma$  producing cells were identified in 4 of 5 dermal crawl-out assays (Christiano 2016). Additionally, data implicate IL-15 in driving activation of IFN-producing CD8 T cells (Xing 2014).

Thus, preclinical and preliminary clinical information, as discussed above, strongly suggests that the primary pathophysiologic mechanism in AA (including AT and AU) is a cytokine mediated (primarily through T-lymphocyte induced upregulation of IL-15 and IFN gamma) induction of and prolonged maintenance of the telogen stage of the hair cycle. Inhibitors of the JAK/STAT pathway, particularly JAK1 and JAK3, are known to downregulate the effects of both IFN-gamma (through the inhibition at JAK1), and IL-15 (through inhibition at both JAK1 and JAK 3), and several published case reports have demonstrated the potential for compounds that are JAK1/3 inhibitors to induce hair growth in patients with AA (Kim 2017, Craiglow, 2014, Gupta 2016, Scheinberg 2016). As ATI-50002 is a potent inhibitor at JAK 1 and JAK 3, it is strongly suggested that ATI-50002 may be effective in the treatment of AA.

Among patients with AA, patients with higher disease burdens are unlikely to have satisfactory outcomes with current therapies. Aclaris Therapeutics, Inc. is developing ATI-50002 as a topical treatment for stable AA. Aclaris is also developing ATI-50001 for the treatment of AU and AT. ATI-50001 is a prodrug that is rapidly converted pre-systemically to ATI-50002, a potent highly selective inhibitor of Janus kinase 1 (JAK1) and Janus kinase 3 (JAK3). In this study, we will be looking to see if topical application of the JAK1/JAK3 inhibitor, ATI-50002, will result in regrowth of eyebrows in areas of loss due to AA, AU or AT.

In a previous Phase 1 study in healthy volunteers, single ascending oral doses of ATI-50001, 50 mg to 500 mg and multiple ascending doses of up to 400 mg BID were well-tolerated. There were no SAEs. All treatment emergent adverse events (TEAEs) were transient and mild in intensity with the exception of 4 TEAEs: facial bone fracture, headache (2), and catheter site pain which were classified as moderate. The most frequently reported drug related TEAEs occurring in >5%

CONFIDENTIAL  
Page 17 of 57

subjects were abdominal pain (10%), flatulence (7%), diarrhea (6%) and headache (6%). Three subjects showed mildly elevated ALT or AST concentrations that were considered not clinically significant. No clinically significant laboratory abnormalities were observed. There were no clinically significant findings from 12-lead ECGs or vital signs assessments.

ATI-50001 was not detected in plasma and there was a dose related increase in plasma of the active metabolite ATI-50002. The half-life of ATI-50002 after 14 days of dosing was approximately 9.0 hours. Systemic levels of ATI-50002, following oral doses of ATI-50001 in healthy volunteers transiently reduced pSTAT5 activity in ex vivo IL-2 stimulated lymphocytes, indicating inhibition of the JAK signaling pathway. Upon multiple dosing, pSTAT5 activity showed a more sustained inhibition during the dosing period.

Non-clinical studies conducted with oral administration of ATI-50001 and topical administration of ATI-50002 support the topical administration of ATI-50002 (ATI-50002 Topical Solution Investigator Brochure August 2017).

### **3.2. Study Rationale**

Preclinical and preliminary clinical information, as discussed above, strongly suggests that the primary pathophysiologic mechanism in AA (including AT and AU) is a cytokine mediated (primarily through T-lymphocyte induced upregulation of IL-15 and IFN gamma) induction of and prolonged maintenance of the telogen stage of the hair cycle. Inhibitors of the JAK/STAT pathway, particularly JAK1 and JAK3, are known to downregulate the effects of both IFN-gamma (through the inhibition at JAK1), and IL-15 (through inhibition at both JAK1 and JAK 3), and several published case reports have demonstrated the potential for compounds that are JAK1/3 inhibitors to induce hair growth in patients with AA. As ATI-50002 is a potent inhibitor at JAK 1 and JAK 3, it is strongly suggested that ATI-50002 may be effective in the treatment of AA.

The purpose of this proof of concept study is to demonstrate the safety, tolerability and efficacy of ATI-50002 Topical Solution, a topical Janus kinase (JAK 1/3) inhibitor in the treatment of unilateral or bilateral loss of eyebrow hair in subjects with AA, AT and AU.

## **4. STUDY OBJECTIVES**

The main objective of this study is to assess the safety, tolerability and efficacy of ATI-50002 Topical Solution 0.46% in subjects with unilateral or bilateral loss of eyebrow hair due to AA, AU or AT.

## **5. SELECTION AND DISPOSITION OF STUDY POPULATION**

### **5.1. Number of Subjects**

Approximately 12 subjects will be enrolled at 1 to 2 sites in the United States.

CONFIDENTIAL  
Page 18 of 57

## 5.2. Study Population Characteristics

Male and female subjects, 18 years of age or older, with a clinical diagnosis of unilateral or bilateral loss of eyebrow hair due to AA, AU or AT, who meet all the inclusion criteria and none of the exclusion criteria will be eligible to enroll in this study.

## 5.3. Inclusion Criteria

To be eligible for the study, subjects must fulfill all the following criteria:

1. Subject is at least 18 years of age.
2. Subject has, based on a subject history and clinical examination, a clinical diagnosis of AA, AU or AT with no eyebrow hair in the affected area(s) and no eyebrow regrowth over the previous 6 months. Affected area is defined as the area(s) of eyebrow hair loss identified at Baseline.
3. Subject has a Clinician Eyebrow Assessment score of 0 (No eyebrow hair in the affected area) for at least one eyebrow.
4. Subject has a Subject Eyebrow Assessment score of 0 (No eyebrow hair in the affected area) for at least one eyebrow.
5. Subject has a duration of the current episode of AA, AU or AT with unilateral or bilateral loss of eyebrow hairs (with at least one distinct patch of  $\geq 30\%$  loss of eyebrow hair) for at least 6 months and no more than seven years prior to Visit 1.
6. Subjects who are Women of Childbearing Potential (WOCBP) must have a negative serum pregnancy test at Screening and a negative urine pregnancy test at Baseline and agree to use a highly effective method of birth control for the duration of the study and for 30 days after last study medication application.
7. Subject is non-pregnant and non-lactating and not planning a pregnancy during the duration of the study and for 30 days after the last study medication application.
8. Subject is in good general health and free of any known disease state or physical condition which, in the opinion of the investigator, would interfere with the study requirements or put the subject at undue risk by study participation.
9. Subject is willing and able to follow all study instructions and to attend all study visits.
10. Subjects taking hormonal replacement therapy must have been on the same dose for at least 6 months prior to Visit 1 and must agree to maintain the same dose for the duration of the study and for 90 days after the last study medication application.
11. Subjects taking thyroid replacement therapy must have been on the same dose for at least 6 months prior to Visit 1 and must agree to maintain the same dose for the duration of the study.
12. Subject agrees to refrain from any eyebrow removal (e.g., plucking, threading, etc.) for the duration of the study.
13. Subject agrees to refrain from any cosmetic surgery (e.g., piercing, tattooing, etc.), on the treatment areas, for the duration of the study.
14. Subject can comprehend and is willing to sign an Informed Consent Form (ICF).
15. Sexually active male subjects must agree to use a barrier method of contraception from the first application of study medication to at least 30 days after the last application of study medication.

CONFIDENTIAL  
Page 19 of 57

#### 5.4. Exclusion Criteria

Any subject who meets one or more of the following criteria will not be included in this study:

1. Subject has, in the opinion of the investigator, permanent eyebrow loss attributed to causes other than AA, AU or AT such as overgrooming, or scarring hair loss.
2. Subject currently has, or has a history of, skin disease in the eyebrow area (e.g., psoriasis, seborrheic dermatitis, etc.) that, in the opinion of the investigator, would interfere with the study medication application or study assessments.
3. Subject has, or has a history of, severe, progressive or uncontrolled autoimmune, metabolic, endocrinologic, renal, hepatic, gastrointestinal, pulmonary, cardiovascular, genitourinary (*i.e.*, renal disease), hematological disease, neurologic or cerebral disorders, infectious disease or coagulation disorders that, in the opinion of the investigator, would put the subject at undue risk by study participation.
4. Subject currently has, or has a history of, proven or suspected systemic or cutaneous malignancy and /or lymphoproliferative disease, other than a history of adequately treated, well healed and completely cleared non-melanoma skin cancers (basal or squamous cell carcinoma) treated successfully at least one year prior to Visit 1.
5. Subject currently has evidence of active or latent bacterial infection, including tuberculosis, or viral infections at the time of enrollment or a history of incompletely treated or untreated tuberculosis. Subjects who have completed therapy for latent tuberculosis may participate.
6. Subject has a history of serious local infection (e.g., cellulitis, abscess) or a systemic infection including but not limited to, pneumonia or septicemia, within 12 weeks prior to Visit 1. Subjects on an antibiotic for a nonserious, acute local infection must complete the antibiotic course prior to enrollment in the study.
7. Subjects positive for HIV, Hepatitis B or C. Subjects with serologic evidence of Hepatitis B vaccination (HepB surface Ab without the presence of HepB surface Ag) will be allowed to participate.
8. Subject currently has or has a known history of herpes zoster or cytomegalovirus (CMV) within 8 weeks prior to Visit 1.
9. Subject has a history of frequent outbreaks of Herpes Simplex Virus, defined as 4 or more episodes per year.
10. Subject has any history of eyebrow tattooing, microblading that in the opinion of the investigator would interfere with the assessment of safety or efficacy.
11. Subject has used any semi-permanent eyebrow coloring (e.g., tinting, dying, etc.) within 6 months prior to Visit 1 that in the opinion of the investigator would interfere with the assessment of safety or efficacy.
12. Clinically significant laboratory abnormalities at Screening that, in the opinion of the Investigator, would make the subject a poor candidate for the study.
13. Subjects with absolute neutrophil count  $<1,000/\text{mm}^3$ , or platelet count  $<50,000/\text{ml}$ .
14. Subject used any of the following therapies within the specified period prior to Visit 1:  
Systemic therapies:

- Disease Modifying Anti-Rheumatic Drugs (DMARDs), Biologics or immunosuppressants, such as: anakinra, adalimumab, azathioprine, glucocorticosteroids, cyclosporine, etanercept, infliximab, methotrexate, TNF inhibitors, ustekinumab, secukinumab, ixekizumab, certolizumab pegol: 4 weeks or 5 half-lives whichever is longer
- Oral retinoids: 12 weeks
- Plaquenil: 8 weeks
- JAK inhibitors (oral or topical): 1 year
- Intralesional steroids on the eyebrow area: 4 weeks

Topical therapies on the eyebrow area:

- Phototherapy, Laser Therapy: 12 weeks
- Anthralin, bimatoprost, glucocorticosteroids, diphenycprone, diphenylcycloprophenone (DPCP), Squaric acid dibutyl ester (SADBE), minoxidil, pimecrolimus, tacrolimus: 4 weeks
- Topical treatments (prescription and over-the-counter) that contain retinoids, retinol, alpha hydroxy acids (e.g. glycolic, lactic acids) and beta hydroxy acids (e.g. salicylic acid) on and around the eyebrow area: 4 weeks

15. Subject has history of sensitivity to any of the ingredients in the study medication.
16. Subject has participated in an investigational drug or device trial in which administration of an investigational study drug or device occurred within 30 days or 5 half-lives (whichever is longer) prior to Visit 1. Subjects who have participated in a study of an investigational drug, device or biologic agent for alopecia areata (AA, AU or AT) within 1 year of screening will be eligible to participate only with individual permission from the Medical Monitor.
17. History of or current alcohol or drug abuse within 2 years of assessment for study enrollment.
18. Screening ECG findings of:
  - QTcF >450msec for males or >470msec for females (use of the ECG algorithm is acceptable for this purpose)
  - Heart rate < 45 or > 100 beats/minutes (inclusive)
  - Rhythm disturbance other than sinus arrhythmia or ectopic supraventricular rhythm (ectopic atrial rhythm)
  - Conduction disturbance including PR >240msec, pre-excitation (delta wave and PR <120msec), second degree or higher AV block
  - Acute or chronic signs of ischemia
  - Left Bundle Branch Block
  - Prior myocardial infarction

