#### 7.2.4. Clinical laboratory sampling

Subjects will go to a local laboratory (to be determined) to have the clinical laboratory tests at Visits 1, 2, 7, 10 and 11. WOCBP will have urine pregnancy tests performed by the study staff at Visit 2, 5, 6, 7, 8, 9, 10 and 11. Approximately 22.5ml of blood will be collected at Visit 1 and 10.5ml for each sample at Visits 2, 7, 10 and 11, a total of approximately 64.5ml per subject for the entire study. The following tests, at a minimum, will be conducted:

Chemistry Panel	Complete Blood Count
Albumin	Hematocrit
Alkaline phosphatase	Hemoglobin
Alanine aminotransferase (ALT)	Platelet count
Aspartate aminotransferase (AST)	Red blood cell morphology
Blood urea nitrogen (BUN)	Red blood cell count
Bicarbonate	White blood cell count
Calcium	White blood cell differential
Chloride	% & absolute
Creatinine	Basophils
Glucose	Eosinophils
Lactate dehydrogenase (LDH)	Lymphocytes
Phosphorus	Monocytes
Potassium	Neutrophils
Sodium	
Total bilirubin	Complete Urinalysis
Total protein	
Uric acid	
Total cholesterol, LDL, HDL	
Triglycerides	

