## 8.2.4. Study Medication Interruption and Discontinuation

### 8.2.4.1 Study Medication Interruption

Treatment with ATI-50002 Topical Solution should be temporarily interrupted in the event of severe adverse events considered related to ATI-50002, or in the event of one or more of the abnormal laboratory values in Table 1.

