**Table 1: Study Medication Interruption Criteria**

Laboratory Test	Interrupt Study Medication if:	Resume Study Medication if:
WBC count	< 2 x 10  /L	≥ 2.5 x 10  /L
ANC	< 1 x 10  /L	≥ 1.5 x 10  /L
Lymphocyte count	< 0.5 x 10  /L	≥ 0.75 x 10  /L
Platelet count	< 75 x 10  /L	≥ 100 x 10  /L
Hemoglobin	< 8 g/dL or decrease > 2 g/dL	≥ 10 g/dL
AST or ALT	> 3 x ULN	< 2 x ULN or within 20% of baseline values
Serum creatinine	>2 x ULN	<1.5 x ULN or within 10% of baseline value

If a subject has one or more of the abnormal laboratory values noted in Table 1, the investigator or designee upon receipt and review of the central laboratory report should instruct the subject to interrupt study medication applications. The investigator or designee should ask the subject about symptoms, concomitant illnesses and medications and repeat the test(s) as soon as possible. The Medical Monitor must be notified of dose interruptions due to SAEs considered related to study medication or laboratory abnormalities noted in Table 1.

If the retest confirms the abnormal laboratory value, then the study medication interruption should continue, followed by repeat testing once a week or sooner at the discretion of the investigator. The subject should be followed until the laboratory abnormality(s) return to normal or to baseline values. Application of study medication may be resumed upon resolution of the abnormal laboratory values to the levels specified in Table 1 above.

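### Exclusion 13's platelet floor, read as 50 × 10⁹/L, lies 25 × 10⁹/L below the count at which the protocol interrupts study medication

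*Combined protocol and SAP*

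**What the plan says.** Criterion 13 appears in the same form in the Synopsis and in Section 5.4. It begins "Subjects with absolute neutrophil count" and excludes neutrophils below 1,000/mm³ or platelets below 50,000, with the platelet unit printed as per ml.

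Section 8.2.4.1 interrupts treatment for severe related adverse events, "or in the event of one or more of the abnormal laboratory values in Table 1". For platelets, Table 1 interrupts below 75 × 10⁹/L and resumes at 100 × 10⁹/L or above. On such a report the investigator "should instruct the subject to interrupt study medication applications", and the resume rule reads: "Application of study medication may be resumed upon resolution of the abnormal laboratory values to the levels specified in Table 1 above". The AST/ALT row also allows resumption "within 20% of baseline values" and the creatinine row "within 10% of baseline value". The platelet row has no such allowance.

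Section 8.2.4.2 stops treatment permanently at platelets below 50 × 10⁹/L, or at a second event below 75 × 10⁹/L, each confirmed by retest.

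Other entry controls bear on a low count but give no platelet number: exclusions 3 and 12, inclusion 8, and the requirement in Sections 6.3.2, 6.6.4 and 7.2.4 that an abnormal result be judged not clinically significant before dosing. Under Section 7.2.4, subjects attend a laboratory "to have the clinical laboratory tests at Visits 1, 2, 7, 10 and 11".

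**The concern.** The protocol sets a number for platelets at entry and another for stopping the drug, and the first is lower than the second. A subject whose count lies between them satisfies criterion 13 and, from the first dose, already meets the rule for interruption. A stable count in that range never reaches the resume level, because resumption is tied to an absolute value and not to the subject's own baseline.

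At stake are short and avoidable exposure in a subject with a low platelet count, an interruption caused by the entry count and not by the drug, and possibly the loss of one subject from a study of about 12 in which dropouts are not replaced (Section 5.8).

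**Working it through.** **Inputs.** Entry floors come from Section 5.4, criterion 13. Interruption and resume limits come from Table 1, and permanent-stop limits from Section 8.2.4.2.

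**Step 1: common unit.** One litre is 10⁶ mm³ or 10³ ml.

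- Neutrophils: 1,000/mm³ × 10⁶ = 1.0 × 10⁹/L.
- Platelets, intended unit: 50,000/mm³ × 10⁶ = 50 × 10⁹/L.
- Platelets, as printed: 50,000/ml × 10³ = 0.05 × 10⁹/L, which is 50 ÷ 0.05 = 1,000 times lower.

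The intended reading is supported by the per-mm³ unit for neutrophils in the same sentence and by the value of 50 × 10⁹/L in Section 8.2.4.2. The rest of the check uses 50 × 10⁹/L, the reading more favourable to the plan.

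**Step 2: thresholds side by side (× 10⁹/L).**

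| Test | Entry floor | Interrupt | Resume | Permanent stop | Interrupt minus entry |
|---|---|---|---|---|---|
| Neutrophils | 1.0 | <1.0 | ≥1.5 | <0.5, or second <1.0 | 1.0 − 1.0 = 0 |
| Platelets | 50 | <75 | ≥100 | <50, or second <75 | 75 − 50 = 25 |

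The neutrophil floor matches the interruption limit; the platelet floor matches the permanent-stop limit. Every count from 50 to <75 passes criterion 13 and meets Table 1's interruption limit.

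**Step 3: rise needed to resume.** From 50, 100 − 50 = 50 (100%). From just under 75, slightly more than 100 − 75 = 25 (25 ÷ 75 = 33%). A subject in the band must therefore rise by more than 25 and up to 50 × 10⁹/L above the entry count.

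**Step 4: path through the study.** Suppose a Visit 1 count of 60 is judged not clinically significant. The Visit 2 sample is drawn on the day of first dosing, and Section 6.3.2 requires only the Visit 1 results to be reviewed beforehand. If the Visit 2 report again shows 60, the interruption rule is met; if that pre-dose sample is not counted, the next scheduled one is Visit 7 (Week 12). A confirmed count keeps treatment interrupted, with repeat tests weekly or sooner. If the count recovers to 100, treatment restarts, and a later confirmed count below 75 ends it. For a count that never recovers, the protocol does not say whether a further low result is a second event or the same one continuing.

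**Step 5: possible effect on efficacy.** Section 6.6.8 removes a subject who cannot apply twice daily for more than 4 consecutive days. Weekly retesting can exceed that. Section 10.1 requires Visit 10 data for the per-protocol set. If the removal rule applies, one such subject would be 1 ÷ 12 = about 8% of planned enrolment.

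**Step 6: after the change.** With a floor of 75, 75 − 75 = 0, as for neutrophils. Correcting the unit alone leaves the band of 25.

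**The case against.** The strongest reply is that no single exclusion lets anyone in. A subject at 50 to <75 × 10⁹/L must also pass exclusion 3 (haematological and coagulation disorders), exclusion 12, inclusion 8 and the clinical-significance review before the first dose. To reach the harm, an investigator must call not clinically significant a count at which the same protocol stops the drug. This largely stands. The review would probably stop most such subjects, and the protocol relies on it alone for the five Table 1 tests that have no numeric entry limit. It does not remove the mismatch: the review is discretionary, and a printed floor of 50 gives some support for passing a count of 60.

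A second reply is that 50 × 10⁹/L has a coherent reading as an absolute floor, since it equals the permanent-discontinuation limit, with judgement applied above it. That is fair. A reader might infer from the neutrophil match that every entry floor was meant to equal its interruption limit, but the documents state no such rule, and one matching row does not establish it. The neutrophil comparison also has limits: a subject entering at 1.0 to <1.5 × 10⁹/L who is later interrupted must likewise exceed the entry count to resume.

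Third, the unit may be a misread microlitre sign in the PDF. That cannot be ruled out, so it is only a query, and the point does not depend on it.

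**Conclusion.** The point holds as a minor inconsistency between two stated thresholds. Read as 50 × 10⁹/L, criterion 13 passes a 25 × 10⁹/L band of platelet counts that already meet the interruption rule; for neutrophils the band is 0. The consequence follows only if the investigator judges such a count not clinically significant.

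Several stronger readings are tempting but not supported:

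- **That the protocol enrols subjects with low platelets, or that the floor serves no purpose.** The other entry controls still apply, and the floor matches the permanent-stop limit.
- **That sites would apply 0.05 × 10⁹/L.** It is not a workable limit.
- **That this is an arithmetic error.** No calculation in the plan is wrong.
- **That efficacy is certainly affected, or certainly not.** Section 6.6.8 does not say whether its 4-day rule covers a laboratory interruption, and Table 1 allows resumption. Section 5.6 calls for final assessments after withdrawal but does not say whether they count as Visit 10 data.

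The documents give no platelet distribution, so the number affected cannot be calculated. With about 12 subjects in good general health, few if any is a reasonable expectation. Retesting and Medical Monitor notification limit the safety consequence.

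**What to change.** In criterion 13, in both the Synopsis and Section 5.4, confirm the platelet unit against the source file, state the limit in × 10⁹/L, and exclude counts below 75 × 10⁹/L (75,000/mm³). Entry and interruption then coincide, as they already do for neutrophils. A floor of 100 × 10⁹/L is not needed: it would only spare subjects entering at 75 to <100 from having to exceed their entry count to resume, and the neutrophil limits leave a similar gap.

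The cost is one line in two places, with the ethics approval that any amendment requires (Section 12.1). The effect on recruitment should be negligible.
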